## **V. STUDY PROCEDURES**

Subjects who have not had an eGFR blood test performed within the previous 90 days will have approximately 10 ml or 2 teaspoons of blood drawn for creatinine testing prior to the scan being performed.

**Subject Screening** - Subjects will be recommended by their treating physician for the study during a clinic visit. The study team member obtaining consent will reinforce with the subjects that participation is voluntary and any decision not to participate will not in any way affect their care, now or in the future. If the subject chooses to participate, the study team member will obtain written informed consent. Any woman of childbearing age, who is seeking to become pregnant, is breastfeeding, or who suspects she may be pregnant, will not be enrolled in the study.

As part of subject screening a genetic test (Ala147Thr TSPO polymorphism genotyping) will be performed. During enrollment subjects will be informed about the genetic testing for study eligibility. If subjects decide to be part of the study and sign the consent, blood will be drawn by the study coordinator. Only those subjects identified as mixed affinity or high affinity from the genetic testing results will continue with PET-CTA imaging. Those subjects who are identified as low affinity will be notified by the study team and will not have PET-CTA scanning performed. Participation in the study will end for the low affinity subjects following the genetic testing.

Any female subject of child bearing potential will have a serum or urine pregnancy test the day of the PET scans.

Any subject under 45 years-old will not be enrolled in this study. No third parties will assist with recruitment of eligible subjects for this protocol.

### **Imaging Details:**

**Positron Emission Tomography (PET)- Computed Tomography Angiography (CTA) –** Eligible participants will undergo F-FDG and C-PBR28 PET-CT and contrast-enhanced CTA imaging performed on the Siemens Biograph 40 PET-CT scanner. All participants will be studied after at least 12-16 hrs of fasting. Subjects will be positioned for maximum comfort on the imaging

table, supine and arms resting above the head or across the chest out of the field of view. PET imaging will begin with  $^{11}\text{C}$ -PBR28. A dosage range of 10-20 mCi is planned. A low-dose CT attenuation scan of the abdomen and pelvis will be acquired for subsequent correction of photon attenuation. Each subject will receive a single intravenous bolus injection of the maximum planned dosage of 20 mCi diluted with normal saline up to a total of 20 mL. The imaging acquisition over the aneurysm site will begin immediately with a ~20-minute dynamic imaging scan. At the end of this imaging scan a 20 min static scan will be performed in the adjacent abdominal or pelvic site (to serve as a reference location). Subject will remain in the scanner for the FDG injection and CT angiography. Subjects will receive an intravenous bolus injection of 10 mCi of  $^{18}\text{F}$ -FDG followed by a 90-minute period prior to reimaging. Next, subjects will receive a standard dose of the Iopamidol contrast agent (50cc) followed by CTA imaging of the abdomen and pelvis using standard acquisition parameters to identify the arterial region of interest (ROI) to determine the blood input function. At the end of the CTA imaging scan, subjects will be removed from the scanner to rest in an uptake room to allow for the decay of  $^{11}\text{C}$ -PBR28. Subjects will be asked to use the restroom to empty their bladder after being removed from the scanner after the CTA imaging and again prior to being repositioned on the imaging table for the FDG scan. A second low-dose CT attenuation will be performed with subsequent ~20-minute dynamic imaging acquisition for FDG. The entire imaging session, including both PET and CT acquisitions, will last up to approximately three hours. The CTA images will be used to identify the arterial region of interest (ROI) for use in determining the blood input function.

Aortic wall  $^{11}\text{C}$ -PBR28 and  $^{18}\text{F}$ -FDG uptake will be considered in terms of standard uptake values (SUV) considering the infrarenal abdominal aorta from the crossing of the left renal vein to the iliac bifurcation. Voxel-wise SUV values over the AAA will be qualitatively assessed across subjects and groups. Maximum (SUVmax) and mean (SUVmean) values normalized to the blood pool and non-aneurysmal thoracic aorta will also be considered. SUVmax and SUV mean values associated with areas of focal uptake will also be considered and compared across subjects and groups using a Student's *t*-test, with  $P = 0.05$  indicating significance.

#### **Image Evaluation:**

Images will be evaluated by an experienced vascular surgeon, who will only evaluate the infrarenal abdominal aorta. Other organs and anatomic structures in the field of view will be evaluated by a radiologist on the study team for incidental findings.

While there is some subjectivity in the manner by which a region of interest (ROI) is determined for image analysis, this study may not be blinded between control and experimental subjects, as control subjects will have non-aneurysmal aortas. However, the analyzing vascular surgeon will be blinded to whether a subject has a small versus a rapidly expanding AAA.

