### **III. SUBJECT SELECTION**

Twenty-four subjects will be recruited for this study. Six control subjects (three males and three females), will be considered. Control subjects will have known atherosclerosis by standard clinical criteria, without aneurysmal disease. Six subjects (three males and three females) with small AAAs

(diameter 3.0-4.5cm), six subjects (three males, AAA >5.5cm and three females, AAA >5.0cm) with AAAs that are indicated for treatment, and six subjects (three males and three females) with rapidly expanding AAAs (>0.5cm over 6 months and/or >1.0cm over 12 months) will be considered. During a clinical visit, the treating physician will introduce the study to each subject, and the study coordinator will provide a comprehensive description and materials to the subject.

Subjects 45 years of age or older will be considered and subjects from any at-risk populations (e.g.: cognitively impaired persons, prisoners) will not be included. A subject will not be eligible for inclusion if any exclusion criteria for PET-CTA apply. Any woman of childbearing age, who is planning to become pregnant, is breastfeeding, and/or suspects she may be pregnant, will not be enrolled in the study.

A subject will not be eligible for inclusion in this study if any of the following criteria apply:

- less than 45 years of age;
- pregnant or breastfeeding;
- any greater than normal potential for cardiac arrest;
- Renal disease – defined as eGFR < 60mg/ml/1.73m^2
- claustrophobic reactions and/or is unable to lie comfortably on a bed inside the scanner for 60 minutes as assessed by physical examination and medical history (e.g. back pain, arthritis);

A TSPO polymorphism has been previously demonstrated, and quantitative interpretations of signal can be confounded by interindividual variability in binding affinity. To avoid this confounder, we will perform Ala147Thr TSPO polymorphism genotyping as part of the screening process. Those subjects identified as mixed affinity or high affinity from the genetic testing results will continue with PET-CTA imaging. Those subjects who are identified as low affinity will be considered screen failures and will not have PET-CTA scanning performed.

Eligibility will be determined by a screening interview and review of the medical record. All subjects recruited for the study will be able to withdraw from the study at any time.

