## **VI. BIOSTATISTICAL ANALYSIS**

This is an exploratory (hypothesis generating) study. Subject Maximum transverse diameters, mean and peak wall stresses, mean and minimum wall strengths, and mean and peak RPI values will be compared between groups using a Students *t*-test, with  $P < 0.05$  indicating significance. Aortic wall  $^{11}\text{C}$ -PBR28 and  $^{18}\text{F}$ -FDG uptake will be considered in terms of standard uptake values (SUV) considering the infrarenal abdominal aorta from the crossing of the left renal vein to the iliac bifurcation. Voxel-wise SUV values over the AAA will be qualitatively assessed across subjects and groups. Maximum (SUVmax) and mean (SUVmean) values normalized to the blood pool and non-aneurysmal thoracic aorta will also be considered. SUVmax and SUVmean values associated with areas of focal uptake will also be considered and compared across subjects and groups using a Students *t*-test, with  $P < 0.05$  indicating significance. Multiplanar and volumetric analyses of coregistered FEA, with  $^{11}\text{C}$ -PBR28 and  $^{18}\text{F}$ -FDG PET images will also be performed. With direct coregistration of the data sets for each subject, qualitative comparisons will be made regarding areas of  $^{11}\text{C}$ -PBR28 and  $^{18}\text{F}$ -FDG uptake, stress, strength, and RPI. Quantitatively, correlations of each data set per subject will be determined.

There will be experimental and control group analysis by comparing subject demographics and aortic image measures. ANOVA with post hoc analyses will be performed to compare the groups.

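### No masking is stated between treatment-size and rapidly expanding AAAs, or to the other tracer and the FEA map, when focal uptake regions are marked

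*Combined protocol and SAP*

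**What the plan says.** Section V, Image Evaluation, gives the reading to one role: "Images will be evaluated by an experienced vascular surgeon, who will only evaluate the infrarenal abdominal aorta". It accepts that "there is some subjectivity in the manner by which a region of interest (ROI) is determined for image analysis". On masking it makes two statements. For controls, "this study may not be blinded between control and experimental subjects, as control subjects will have non-aneurysmal aortas". Among aneurysm subjects, "the analyzing vascular surgeon will be blinded to whether a subject has a small versus a rapidly expanding AAA".

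There are four groups of six. Section III includes "six subjects (three males, AAA >5.5cm and three females, AAA >5.0cm) with AAAs that are indicated for treatment", and this group does not appear in the masking text. Small AAAs are 3.0 to 4.5 cm. The rapidly expanding group is defined only by growth ("rapidly expanding AAAs (>0.5cm over 6 months and/or >1.0cm over 12 months"), with no diameter limits.

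Section VI says that focal SUVmax and SUVmean "values associated with areas of focal uptake will also be considered and compared across subjects and groups" by t-test. It also plans qualitative comparison of both tracers with stress, strength and RPI on co-registered data, and correlations of the data sets within each subject. It adds no rule on masking, reading order or reader agreement. Under FEA Interpretation, the analysis is done at another institution from PET-CTA discs that carry a study ID only.

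**The concern.** Focal SUVmax and SUVmean depend on what the reader calls focal, and the plan gives no rule for that. A reader who knows the group may look harder for focal uptake, or draw regions differently, in the group expected to show it. Section II predicts that the pattern will be most pronounced in rapidly expanding AAAs, so the direction of any expectation is already set.

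The second exposure is between image types. Section II predicts that the two tracers will correlate and that focal PBR28 uptake will lie where RPI is greatest and wall strength lowest. If focal PBR28 regions are marked with the FDG image or the RPI map in view, the agreement seen may partly reflect the marking. No later statistical adjustment can separate the two.

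Aim 2 uses these patterns to judge whether to extend the analyses to a larger group, so agreement produced by the reading procedure could misdirect that decision.

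**Working it through.** **1. Masking by pair of groups.** Four groups make 4 × 3 / 2 = 6 pairs. The middle column is from Image Evaluation; the last follows from the diameters and growth rules in Section III.

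| Pair | Masking stated | Does diameter on CTA separate them? |
|---|---|---|
| Control v each AAA group (3 pairs) | May not be masked | Yes |
| Small v rapidly expanding | Masked | Only if the rapid AAA is above 4.5 cm |
| Small v treatment-size | Not mentioned | Yes: 3.0 to 4.5 cm against >5.0 cm (women) or >5.5 cm (men) |
| Treatment-size v rapidly expanding | Not mentioned | Not if the rapid AAA is also above the treatment size |

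So one pair is masked, three are declared possibly unmasked, and two are not addressed. Of those two, small versus treatment-size cannot be masked in practice. Treatment-size versus rapidly expanding can be, wherever the diameters overlap. A rapid AAA between 4.5 cm and the treatment size belongs to neither size group, so diameter alone can identify it whatever rule is written.

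**2. Masking between image types.** Image Evaluation, FEA Interpretation and Section VI contain no reading order, no separate reading of the two tracers and no rule withholding FEA output. The Project Timeline puts co-registered FEA and PET in months 1 to 8 and pattern comparison in months 9 to 10, with no earlier step that fixes the PET regions. The study-ID labelling applies to discs sent to the FEA site, not to the surgeon's reading.

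**3. Outcomes exposed.** Whole-segment SUV runs from the left renal vein crossing to the iliac bifurcation, so its limits do not depend on a judgement of what is focal. Stress, strength and RPI come from CTA and do not change with the PET regions. The exposure is therefore to focal SUVmax and SUVmean and to the co-location comparison.

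**4. Illustration of size.** The documents give no figure for reader bias, so the shifts below are assumptions. Take two groups of 6, no true difference, a reader-induced shift of b SD in one group, and a two-sided t-test at 0.05 (the documents do not state sidedness). Then

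- degrees of freedom = 2 × 6 − 2 = 10
- noncentrality = b × √(6/2) = 1.732 b
- false-positive rate = P(|T| > t critical), where T is noncentral t

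| b (assumed) | Noncentrality | False-positive rate |
|---|---|---|
| 0 | 0 | 5.0% |
| 0.25 | 0.433 | 6.8% |
| 0.5 | 0.866 | 12.3% |
| 0.75 | 1.299 | 21.8% |
| 1.0 | 1.732 | 34.7% |

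This covers bias from knowing the group only. It says nothing about how far seeing the other images would inflate co-location, for which the documents offer no basis for a figure. The plan's own sample-size figure (about 10 per group needed) cannot be reproduced, as no effect size or SD is given; this point does not rest on it.

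**The case against.** A reader might infer that the surgeon will see the treatment-size label, the other tracer and the FEA map. The documents do not say so; what can be said is that no masking is stated. That the surgeon draws the regions is also an inference, from the reference to the analyzing surgeon next to the sentence on region choice.

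A reader might also infer that all three AAA groups could be masked from one another. They could not, because small and treatment-size AAAs do not overlap in diameter. In addition, a reader masked to small versus rapidly expanding must already be denied growth history for those subjects. If that were applied to every AAA subject, it would largely hide the treatment-size versus rapid distinction too. This narrows the gap in group masking to an unnamed group, which a wording change can close.

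It would be too strong to say that the reading procedure manufactures the agreement. FEA is done off site from CTA, whole-segment SUV has fixed landmarks, and the voxel-wise assessment and within-subject correlations are not stated to depend on focal regions. The study is also described as exploratory, with no intended effect on management.

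These limits stand, and they confine the point to focal measures and co-location. They do not remove it. Image Evaluation is where masking is specified, P < 0.05 is still to be called significant, and co-location is the hypothesis itself. One further limit is that the FEA site receives the PET data, so locking the PET regions protects one direction only.

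**Conclusion.** The point holds in limited form. The plan accepts that region choice is subjective and states a mask for one of six group pairs. It leaves unaddressed the one other pair that could usefully be masked, and does not require focal regions to be marked without sight of the other tracer or the FEA map. Following it as written can bias the focal SUV comparisons and can inflate apparent PBR28/FDG/RPI co-location.

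The size is unknown. Under the assumed shifts, the false-positive rate for one focal-SUV t-test would lie between about 7% (0.25 SD) and 35% (1.0 SD). The conclusion assumes that the analyzing surgeon marks the focal regions and that no unstated procedure already withholds this information. It does not extend to whole-segment SUV or to the FEA measures. This is a cheap improvement, not a flaw that invalidates an exploratory study.

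**What to change.** Amend Section V, Image Evaluation, as follows.

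- The same reader works from re-coded, randomly ordered images, with group label and growth history withheld for all AAA subjects, including the treatment-size group.
- Focal PBR28 and focal FDG regions are drawn in separate passes, each without sight of the other tracer.
- Both sets of regions are locked before FEA results are opened and before any co-registered comparison. Because FEA is done off site, this order is practicable, and the co-registered analyses in Section VI can then proceed on the locked regions.
- State that control status and visible diameter, and therefore small versus treatment-size, cannot be masked.

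The cost is staff time to re-code files and enforce the reading order, with a short delay before co-registered review. No extra reader, subject or scan is needed.

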#### **FEA Interpretation:**

FEA will be performed by [name] group at the University of Pittsburgh. PET-CTA scans performed for the study will be copied onto CD, labeled with a study ID only and mailed by a member of the Washington University Study team. No PHI will be provided to University of Pittsburgh. The PET-CTA scans and FEA performed by [name] laboratory at the University of Pittsburgh will be saved for possible future analysis or data presentation.

## **VI. BIOSTATISTICAL ANALYSIS**

This is an exploratory (hypothesis generating) study. Subject Maximum transverse diameters, mean and peak wall stresses, mean and minimum wall strengths, and mean and peak RPI values will be compared between groups using a Students *t*-test, with  $P < 0.05$  indicating significance. Aortic wall  $^{11}\text{C}$ -PBR28 and  $^{18}\text{F}$ -FDG uptake will be considered in terms of standard uptake values (SUV) considering the infrarenal abdominal aorta from the crossing of the left renal vein to the iliac bifurcation. Voxel-wise SUV values over the AAA will be qualitatively assessed across subjects and groups. Maximum (SUVmax) and mean (SUVmean) values normalized to the blood pool and non-aneurysmal thoracic aorta will also be considered. SUVmax and SUVmean values associated with areas of focal uptake will also be considered and compared across subjects and groups using a Students *t*-test, with  $P < 0.05$  indicating significance. Multiplanar and volumetric analyses of coregistered FEA, with  $^{11}\text{C}$ -PBR28 and  $^{18}\text{F}$ -FDG PET images will also be performed. With direct coregistration of the data sets for each subject, qualitative comparisons will be made regarding areas of  $^{11}\text{C}$ -PBR28 and  $^{18}\text{F}$ -FDG uptake, stress, strength, and RPI. Quantitatively, correlations of each data set per subject will be determined.

There will be experimental and control group analysis by comparing subject demographics and aortic image measures. ANOVA with post hoc analyses will be performed to compare the groups.

### **Power Calculation:**

From clinical experience, we expect total 24 subjects, approximately six subjects (3 men and 3 women) with small AAA size that will continue to undergo surveillance (3.0-4.5cm), six subjects (3 men and 3 women) with AAAs that will undergo treatment, and six subjects (3 men and 3 women) with rapidly expanding AAAs (>0.5cm over 6 months and/or >1.0cm over 12 months). Control group will be consist of 6 subjects (3 men and 3 women) with known atherosclerosis, by nature of carotid stenosis and no aortic aneurismal dilation. Since this is an exploratory study, there is no definite power calculation for qualitative measures but quantitative analysis for continues variables, to reach a power of 0.80 with confidence level of 95% at alpha level of 0.05, there are approximately 10 subjects are needed per group. This is a small exploratory study, and we will limit the subject enrollment to six subjects per group due to the financial reasons.

Statistical analysis will be performed using the SAS statistical package (SAS Institute Inc., Cary, NC).

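### Does the power paragraph mislead by quoting 0.80 power for 10 per group when only six per group are enrolled?

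*Combined protocol and SAP*

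**What the plan says.** Section III fixes the total: "Twenty-four subjects will be recruited for this study", in four groups of six (controls, small aneurysms, aneurysms due for treatment, rapidly expanding aneurysms).

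The Power Calculation paragraph in section VI says there is no definite power calculation for the qualitative measures. For continuous variables it says that "to reach a power of 0.80 with confidence level of 95% at alpha level of 0.05, there are approximately 10 subjects are needed per group". It then calls this a small exploratory study and states that "we will limit the subject enrollment to six subjects per group due to the financial reasons". It does not give the variable, the difference, the SD, the sidedness or the test behind the 10, or the power at six.

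The main text of section VI opens by labelling the study exploratory and hypothesis generating. It plans Student's t-tests at P<0.05 for diameter, wall stress, wall strength, rupture potential index (RPI) and focal uptake values. It also says that "ANOVA with post hoc analyses will be performed to compare the groups", without naming the post hoc method.

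**The concern.** The only power figure in the document belongs to a sample size the study will not enrol. A reader who sees 0.80 may carry it over to the 24 subjects. With no effect size stated, nobody can work out what six per group can detect without guessing how the 10 was obtained. The figure may also fit only one of the two planned analyses: a two-group calculation does not carry over to multiplicity-adjusted comparisons among four groups.

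Aim 2 in section II is to judge whether a larger study is appropriate. If a non-significant contrast in RPI or in uptake of the investigational tracer were taken as no signal, a large true difference could be dismissed because the study was too small to show it reliably.

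**Working it through.** **Inputs.** From the Power Calculation paragraph: power 0.80, alpha 0.05, about 10 per group needed, six per group enrolled. From section III: four groups, 24 subjects. Not stated: effect size, SD, variable, sidedness, test. Two-sided testing is assumed first, in line with the 95% confidence level.

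**1. Can the 10 be reproduced?** No. There is no effect size to put in, so it can only be inverted.

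- Two-sided two-sample t-test, noncentral t with noncentrality d × sqrt(n/2): n = 10 and power 0.80 give d = 1.325.
- Normal approximation: d = (1.960 + 0.842) × sqrt(2/10) = 1.253.

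A value of 10 is therefore consistent with a large standardised difference. Nothing shows it to be wrong.

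**2. Power at six per group for the implied difference.** With d = 1.325, noncentrality = 1.325 × sqrt(6/2) = 2.295. On 10 df the critical value is 2.228 and the power is 0.545. A simulation of 200,000 runs gave 0.546.

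**3. Sensitivity to how the 10 was obtained.**

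| Assumed origin of the 10 | Implied effect | Power at six |
|---|---|---|
| Two-sided t-test | d = 1.325 | 54.5% |
| Two-sided normal approximation | d = 1.253 | 58.3% |
| One-sided t-test | d = 1.156 | 58.7% |
| One-sided normal approximation | d = 1.112 | 61.1% |
| Four-group F test | f = 0.551 | 51.9% |
| Two-sided t-test, n really 9 | d = 1.407 | 59.5% |
| Two-sided t-test, n really 11 | d = 1.256 | 50.2% |
| Tukey, four groups | d = 1.591 | 49.7% |

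The range is about 50% to 61%.

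**4. Sensitivity to the analysis, keeping d = 1.325 and six per group.**

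- Pooled ANOVA error (20 df), unadjusted: 58.9%.
- Tukey, with studentized range value 3.958, so the critical t is 3.958/sqrt(2) = 2.799: 33.4% (simulation 33.4%).
- Bonferroni for six pairs: 29.5% with pooled error, 23.4% with separate t-tests.
- Scheffé: 26.0%.

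The adjusted figures combine an effect calibrated on an unadjusted test with a stricter test. They depend on a post hoc method that the plan does not choose.

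**5. Detectable difference at 80% power with six per group.** 1.80 SD (t-test), 1.70 SD (pooled, unadjusted), 2.13 SD (Tukey).

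**6. Precision of an estimated difference, half-width of the 95% interval.**

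- Two-group t: 2.228 × sqrt(2/6) = 1.29 SD.
- Pooled ANOVA error: 2.086 × sqrt(2/6) = 1.20 SD.
- Tukey: 2.799 × sqrt(2/6) = 1.62 SD.

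**7. Does the text contradict itself?** One sentence says 10 are needed for 0.80; the next says six will be enrolled because of cost. Read together, they say that 0.80 will not be reached. No sentence attributes 0.80 to six.

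**The case for a change.** The strongest case for a change is that admitting six is fewer than 10 does not tell the reader what six can detect. The plan keeps a significance threshold of 0.05, and Aim 2 looks ahead to a larger study. At about 1.3 SD, a two-group t-test misses the difference 1 − 0.545 = 45.5% of the time, and a Tukey comparison misses it 1 − 0.334 = 66.6% of the time. Subjects receive radiation for research only and can expect no direct benefit, so the limits of the data deserve a plain statement. The remedy would cost only a sentence or two and need no further enrolment.

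The arithmetic stands, and so does the observation that the assumptions behind the 10 are missing. The consequence does not. The approach under Aim 2 describes qualitative comparisons, no rule links expansion of the research to a P value, and nothing in the plan treats a non-significant result as absence of a difference. Extra wording would guard against a reading that the plan does not make. Nor is it right that the 10 fits no planned analysis: Student's t-test is named in section VI for the main quantitative measures, so a t-test-based size matches one of them. Tukey is named nowhere, so the 33% is only an illustration.

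**Conclusion.** The concern identifies missing detail, not an error, and no change to the plan is called for. No stated power, sample size or property of the design is shown to be false: the 10 cannot be tested without its inputs, and the plan openly enrols fewer for a stated financial reason. In an exploratory study of 24 subjects that is a fair trade-off.

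If the 10 came from a two-sided two-sample t-test, power at six per group for the implied 1.32 SD is about 54%. The alternative derivations examined put it between about 50% and 61%. Under that t-test, 80% power is reached at about 1.8 SD. The Tukey figures, about 33% and 2.1 SD, hold only if that method were chosen. Adding these numbers to the paragraph would change no comparison, estimate or conclusion. An analyst reporting group differences with 95% intervals, about 1.2 to 1.3 SD either side without adjustment, would show the reader how little six per group can settle.
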